Attachment 3. Protocol AACD Blood Sampling Summary

These tables summarize the maximum number of venipunctures and blood volumes for all blood sampling (screening, safety laboratories, and bioanalytical assays) during the study. Fewer venipunctures and blood draws may actually occur, but this will not require a protocol amendment.

Protocol I5T-MC-AACD Sampling Summary Part A (Cohorts 1 and 2)

Purpose	Maximum Blood Volume per Sample (mL)	Maximum Number of Blood Samples	Maximum Total Volume (mL)
Screening tests ^a	26	1	26
Clinical laboratory tests ^a	12	9	108
Coagulation tests	6	1	6
Drug assays ^b	4	17 (+3)	68 (12)
Blood discard for cannula patency	3	15	45
Immunogenicity assessments ^a	10	10	100
Pharmacogenetic sample ^c	11	1 (+1)	11 (11)
Nonpharmacogenetic/biomarker samples	21	2	42
Blood sample for exploratory immune safety ^a	14	2	28
Total			434 (457)
Total for clinical purposes (rounded to the nearest 10 mL)			440 (460)

^a Additional samples may be drawn if needed for safety purposes.

^b A maximum of 3 blood samples per patient may be drawn at additional time points during the study, if warranted and agreed upon between both the investigator and sponsor.

^c An additional sample may be taken postdose if required.

Protocol I5T-MC-AACD Sampling Summary Part A (Cohort 3)

Purpose	Maximum Blood Volume per Sample (mL)	Maximum Number of Blood Samples	Maximum Total Volume (mL)
Screening tests ^a	26	1	26
Clinical laboratory tests ^a	12	9	108
Coagulation tests	6	1	6
Drug assays ^b	4	13 (+3)	52 (12)
Blood discard for cannula patency	3	11	33
Immunogenicity assessments ^a	10	6	60
Pharmacogenetic sample ^c	11	1 (+1)	11 (11)
Nonpharmacogenetic/biomarker samples	21	2	42
Blood sample for exploratory immune safety ^a	14	2	28
Total			366 (389)
Total for clinical purposes (rounded to nearest 10 mL)			370 (390)

a Additional samples may be drawn if needed for safety purposes.

b A maximum of 3 blood samples per patient may be drawn at additional time points during the study, if warranted and agreed upon between both the investigator and sponsor.

c An additional sample may be taken postdose if required.

Protocol I5T-MC-AACD Sampling Summary Part B (Cohorts 4 and 5)

Purpose	Maximum Blood Volume per Sample (mL)	Maximum Number of Blood Samples	Maximum Total Volume (mL)
Screening tests ^a	26	1	26
Clinical laboratory tests ^a	12	14	168
Coagulation tests	6	2	12
Drug assays ^b	4	40 (+3)	160 (12)
Blood discard for cannula patency	3	20	60
Immunogenicity assessments ^a	10	10	100
Pharmacogenetic sample ^c	11	1 (+1)	11 (11)
Nonpharmacogenetic/biomarker samples	21	5	105
Blood sample for exploratory immune safety ^a	14	4	56
Total			698 (721)
Total for clinical purposes (rounded to nearest 10 mL)			700 (730)

a Additional samples may be drawn if needed for safety purposes.

b A maximum of 3 blood samples per patient may be drawn at additional time points during the study, if warranted and agreed upon between both the investigator and sponsor.

c An additional sample may be taken postdose if required.

Protocol I5T-MC-AACD Sampling Summary Part C (Cohorts 6 and 7)

Purpose	Maximum Blood Volume per Sample (mL)	Maximum Number of Blood Samples	Maximum Total Volume (mL)
Screening tests ^a	26	1	26
Clinical laboratory tests ^a	12	21	252
Coagulation tests	6	2	12
Drug assays ^b	4	36 (+3)	144 (12)
Blood discard for cannula patency	3	25	75
Immunogenicity assessments ^a	10	12	120
Pharmacogenetic sample ^c	11	1 (+1)	11 (11)
Nonpharmacogenetic/biomarker samples	21	7	147
Blood sample for exploratory immune safety ^a	14	6	84
Total			871 (894)
Total for clinical purposes (rounded to nearest 10 mL)			880 (900)

a Additional samples may be drawn if needed for safety purposes.

b A maximum of 3 blood samples per patient may be drawn at additional time points during the study, if warranted and agreed upon between both the investigator and sponsor.

c An additional sample may be taken postdose if required.

Attachment 4. Protocol AACD Blinding/Unblinding Plan

Levels of unblinding are indicated in the table below. This table provides general guidance as to who will be allowed access to randomization codes at various steps of the trial. The information elsewhere in the protocol will always take precedence over this table. For interim analysis, appropriate interim analysis team members, including a statistician, a programmer, and a data manager, will be identified and agreed upon between Lilly and the TPO.

Randomization data are kept strictly confidential and are accessible only by authorized personnel until unblinding of the trial as described below. All measures possible must be taken to maintain the blind, which means that access to the randomization code must be restricted to authorized personnel as described in the protocol and summarized in the table below.

[figure not shown]
If there is a need for unblinding of select people from Lilly and/or the TPO who are not in direct contact with the site, the detailed process, including formation of the unblinded team, creating restricted access electronic folders, and measures taken to guard against inappropriate dissemination of treatment codes (for example, by maintaining no contact with the study team until team is unblinded), will be described in the unblinding plan or another appropriate document and approval sought from Lilly and Covance team statisticians.

Study I5T-MC-AACD Blinding and Unblinding Plan

Study Team Member	Study Timelines				
	Screening	Randomization	Treatment Phase	Follow-Up	Database Lock
General					
Drug supply	NA	U	U	U	U
Randomization statisticians	NA	U	U	U	U
ECG reader	NA	U	U	U	U
Bioanalysis lab/sample analysis	NA	U	U	U	U
Clinical site					
Pharmacist	NA	U	U	U	U
Dosing nurse	NA	B	B	B	B
Patient	NA	B	B	B	B
CP/investigator	NA	B	B	B	U
Study monitor	NA	U	U	U	U
Covance Early Clinical Biometrics					
Project integration	NA	U	U	U	U
Data management	NA	U	U	U	U
Programming	NA	U	U	U	U
Statistician	NA	U	U	U	U
Medical writing	NA	U	U	U	U
Pharmacokinetic scientist/associate	NA	U	U	U	U
Lilly					
CPM	NA	U	U	U	U
CPA/CPC	NA	U	U	U	U
DSA	NA	U	U	U	U
SDTM core team	NA	U	U	U	U
Statistician	NA	U	U	U	U
Medical writing	NA	U	U	U	U
CP	NA	U	U	U	U
CRP	NA	U	U	U	U
Pharmacokinetic scientist/associate	NA	U	U	U	U
Pharmacovigilance personnel	NA	U	U	U	U

Abbreviations: B = blinded; CP = clinical pharmacologist; CPA/CPC = clinical pharmacology associate/clinical pharmacology consultant; CPM = clinical project manager; CRP = clinical research physician; DSA = data sciences associate; ECG = electrocardiogram; lab = laboratory; NA = not applicable; SDTM = study data tabulation model; U = unblinded.

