9.6. Blinding

This is a patient- and investigator-blind study.

To preserve the blinding of the study, a minimum number of Lilly personnel will see the randomization table and treatment assignments before the study is complete. Refer to [Attachment 4](#) for details on the blinding/unblinding plan.

Emergency codes will be available to the pharmacy. A code, which reveals the treatment group for a specific study patient, may be opened during the study only if the patient's well-being requires knowledge of the patient's treatment assignment.

If a patient's study treatment assignment is unblinded, the patient must be discontinued from the study, unless the investigator obtains specific approval from a Lilly clinical pharmacologist or CRP for the study participant to continue in the study. During the study, emergency unblinding should occur only by accessing the study patient's emergency code.

In case of an emergency, the investigator has the sole responsibility for determining if unblinding of a patient's treatment assignment is warranted. Patient safety must always be the first consideration in making such a determination. If the investigator decides that unblinding is warranted, the investigator should make every effort to contact the Lilly clinical pharmacologist or CRP prior to unblinding a study patient's treatment assignment. If a study patient's treatment assignment is unblinded, Lilly must be notified immediately.

Upon completion of the study, all codes must be returned to Lilly or its designee.

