10.6.3.4. Electrocardiograms

For each patient, a single 12-lead digital ECG will be collected according to the Study Schedule ([Attachment 1](#)). ECGs must be recorded before collecting any blood for safety or PK tests. Patients must be supine for approximately 5 to 10 minutes before ECG collection and remain supine but awake during ECG collection.

All ECGs, except for the screening ECG, will be obtained in triplicate at approximately 1-minute intervals.

ECGs may be obtained at additional times, when deemed clinically necessary. Collection of additional ECGs at a particular time point is allowed to ensure high quality records. All ECGs recorded should be stored at the investigational site.

ECGs will be interpreted by a qualified physician (the investigator or qualified designee) at the site as soon after the time of ECG collection as possible, and ideally while the patient is still present, to determine whether the patient meets entry criteria at the relevant visit(s) and for immediate patient management, should any clinically relevant findings be identified.

If a clinically significant quantitative or qualitative change from baseline is identified (including, but not limited to, changes in QT/corrected QT [QTc] interval from baseline) after enrollment, the investigator will determine whether the patient can continue in the study. The investigator or qualified designee is responsible for determining whether any change in patient management is needed and must document his/her review of the ECG printed at the time of evaluation from at least 1 of the replicate ECGs from each time point. Any new clinically relevant finding should be reported as an AE.

Digital ECGs will be electronically transmitted to a central ECG laboratory designated by Lilly. The central ECG laboratory will perform a basic quality control check (for example, demographics and study details) then store the ECGs in a database. At a future time, the stored ECG data may be overread at the central ECG laboratory for further evaluation of machine-read measurements or to meet regulatory requirements.

The machine-read ECG intervals and heart rate may be used for data analysis and report writing purposes unless a cardiologist overread of the ECGs is conducted before completion of the final study report (in which case the overread data would be used).

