10.6.3.7. Magnetic Resonance Imaging

MRI scans will be obtained at time points indicated in the Study Schedule ([Attachment 1](#)).

MRI safety monitoring will consist of MRIs with sequences appropriate for detecting vasogenic edema and microhemorrhage (ARIA-E and ARIA-H). The number of microhemorrhages detected on the baseline MRI scan will serve as 1 factor in the exclusion criteria (that is, exclusion of patients with >4 microhemorrhages). Microhemorrhages might indicate a higher risk for macrohemorrhage, as well as the presence of significant amyloid angiopathy, and there appears to be a risk of microhemorrhage with some antiamyloid treatments in preclinical models and possibly in humans as well.

The determination of the number of microhemorrhages will be required to be assessed on a 1.5T or 3T MRI using a T₂*-weighted gradient-echo sequence. Additional FLAIR images will be performed to evaluate for the presence of vasogenic edema. All baseline and safety imaging will be analyzed by a central reader blinded to treatment.

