11.2.7.2. Statistical Evaluation of Safety

Safety parameters that will be assessed include safety laboratory parameters, vital signs, and ECG parameters. The parameters will be listed and summarized using standard descriptive statistics. Additional analysis will be performed if warranted upon review of the data.

A shift table for each dose group will be constructed to assess the MRI measurement pre- and postdose for changes and additions of vasogenic edema and microhemorrhages.

Suicide-related thoughts and behaviors based on the C-SSRS will be listed by patient. Only time points and patients that show ideation/behavior of suicide will be displayed (ie, all “no” responses will not be displayed).

Exploratory analyses of Fridericia’s corrected QT interval data from ECG monitoring in a Phase 1 trial are performed to judge the extent and/or risk of QT prolongation. There will be an exploratory assessment of potential prolongation by examining mean change in Fridericia’s corrected QT interval as a function of serum drug concentration obtained and an inspection of the upper confidence limit relative to a value of 10 msec, which is consistent with International Conference on Harmonisation (ICH) guidance. Frequency tables of QTc changes from baseline and large QTc values may also be obtained in accordance with ICH guidance.

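### The blinding plan gives the ECG reader access to treatment codes from randomization on, so if the optional cardiologist overread is done, the exploratory QTcF assessment could rest on readings made with treatment known

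*Protocol*

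**What the plan says.** Attachment 4 of the protocol tabulates blinding status by role and study stage. Under the General block it has the row "ECG reader NA U U U U". The columns are screening, randomization, treatment phase, follow-up and database lock, and the key gives U as unblinded. The attachment describes its own status in two sentences: "This table provides general guidance as to who will be allowed access to randomization codes at various steps of the trial" and "The information elsewhere in the protocol will always take precedence over this table".

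Protocol 10.6.3.4 describes two kinds of ECG reading. For eligibility and immediate patient management, the investigator or a qualified designee interprets the tracing at the site. The digital tracings also go to a central ECG laboratory, which checks and stores them and may overread them later. Machine-read intervals may be used for analysis and reporting "unless a cardiologist overread of the ECGs is conducted before completion of the final study report (in which case the overread data would be used".

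Protocol 11.2.7.2 plans an exploratory look at mean change in QTcF against serum concentration, with "an inspection of the upper confidence limit relative to a value of 10 msec". SAP 4.2.7.2 repeats this.

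For the other centrally read safety measure, Protocol 10.6.3.7 is explicit: "All baseline and safety imaging will be analyzed by a central reader blinded to treatment".

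**The concern.** Many roles in Attachment 4 are unblinded, which fits a study that is blind only to patient and investigator. Most of those roles handle, supply or report data. An ECG reader is different, because an overread produces the measurement that is then analysed. If that reader may consult the codes, treatment knowledge can enter the QT values themselves, and no later step in the analysis would remove it.

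What is at stake is the credibility of the QTcF assessment, in either direction: a reading effect aligned with treatment could imitate a prolongation or hide one. The plan has already accepted this principle for imaging, where the central reader is blinded, so the different treatment of ECGs looks unintended.

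**Working it through.** No figure in the plan needs reproducing. The check sets the relevant sections side by side, followed by a short piece of algebra on what kind of reading shift would matter.

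1. **Is the reader allowed the codes?** Yes. The Attachment 4 row is U at randomization, treatment phase, follow-up and database lock. By contrast, the investigator row is B until database lock.

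2. **Does other text override the table?** The table gives way to the rest of the protocol, so each candidate was checked.
   - Protocol 9.6 names only patient and investigator as blind. Its limiting sentence, that "a minimum number of Lilly personnel will see the randomization table and treatment assignments before the study is complete", is about sponsor staff and does not clearly reach a central laboratory that the sponsor designates.
   - Protocol 10.6.3.4 says nothing on blinding of the overread.
   - Protocol 10.6.3.7 blinds the imaging reader only.
   - SAP Section 5 refers back to Attachment 4.

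   No statement blinds the ECG reader, so the U entries stand.

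3. **Do the overread values reach an analysis?** Only conditionally. The overread is optional and undated. If it is completed before the final study report, its values are the ones used. If it is not done, the machine values are used.

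4. **Which analysis?** The exploratory QTcF work in Protocol 11.2.7.2 and SAP 4.2.7.2. The primary objective is florbetapir imaging and does not depend on ECG reads.

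5. **Does anyone need this reader unblinded?** The documents show no such need. Emergency codes are held by the pharmacy (Protocol 9.6). Suspension of dosing is judged by the unblinded sponsor physician or clinical pharmacologist (Protocol 8.2.1.3). The start of later cohorts is agreed between investigator and sponsor (Protocol 9.4.1).

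6. **What form of shift would bias the result?** Write the recorded QTcF of patient i at time t as Y(i,t) = T(i,t) + s(i,t), where T is the true value and s the reading shift. The change from baseline is

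   Y(i,t) − Y(i,0) = [T(i,t) − T(i,0)] + [s(i,t) − s(i,0)].

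   - If s is the same on every tracing of a patient, the second bracket is zero. The schedule includes predose tracings and time-matched tracings before the first dosing day, so a baseline exists from which such a shift would cancel.
   - If s differs between baseline and postdose tracings by an amount d in patients known to be on active drug, their mean change moves by d. In this simplest case an upper limit m + h (mean change plus half-width) becomes m + d + h, so the distance to 10 msec changes from 10 − (m + h) to 10 − (m + h) − d.
   - The shift d is systematic, so a larger sample narrows h but leaves d untouched.

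   The documents give no value or range for d, and no reader variability from which one could be derived. The calculation stops here.

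**The case against.** The case on the other side is substantial, and most of it limits the point without removing it.

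- **The overread may never happen.** This stands. The default is machine-read intervals, and without an overread the table row has no effect on the analysis. A reader might infer that the QT conclusion will rest on unblinded readings; the documents support only that it could.
- **The analysis is exploratory.** This stands. Neither document plans a formal claim that QT prolongation is absent.
- **Permission is not knowledge at the moment of reading.** This stands in part. Attachment 4 is guidance on access to codes and does not say that tracings are read with treatment attached. Nor does it define the ECG reader as the overreading cardiologist. The row does sit under General, apart from the clinical site staff, and site reads belong to the investigator or designee, so the central reader is the natural interpretation. The attachment also refers to a separate unblinding plan for selected sponsor and contractor staff; whether that covers the ECG laboratory cannot be seen from here.
- **A shift might cancel.** This stands for a shift that is constant within a patient, as shown above. It does not stand for one that differs between baseline and postdose tracings by treatment. A reader might be tempted to set an assumed shift of a few msec against the 10 msec value, but nothing in the documents supports any such figure.
- **Patients are protected anyway.** This also stands. A reader might infer that individual safety decisions depend on the unblinded reader. They do not on this text: management reads are made at the site, and the investigator is blinded until database lock.

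None of these points supplies a statement that the overread is blinded, or a reason for it not to be.

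**Conclusion.** The point holds as a conditional one. The plan allows the ECG reader access to treatment codes, lets an overread displace the machine values, and nowhere requires that overread to be blinded. If an overread is done before the final report, the exploratory QTcF assessment is open to an assessment bias that could be avoided.

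The conclusion rests on two assumptions: that the ECG reader in Attachment 4 is, or includes, the person doing the central overread, and that no document outside those reviewed blinds that person. The size of any bias is unknown and cannot be bounded from the documents. The primary imaging result and patient-level ECG decisions are not affected. The correction is worth making because it costs little and brings ECG reading into line with the imaging rule.

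**What to change.** Make two changes together.

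1. In Attachment 4, set the ECG reader row to B at randomization, treatment phase and follow-up, and keep it B until any overread is complete. The last part matters because 10.6.3.4 allows an overread up to completion of the final study report, which may come after database lock. Changing to U at lock alone could leave a gap.
2. In Protocol 10.6.3.4, add: *Any central overread used for analysis will be done blinded to treatment assignment.* This mirrors the rule for imaging in 10.6.3.7, and it is needed because the table is only guidance and gives way to the main text.

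The cost is one table row, one sentence and an instruction to the central ECG laboratory. Site reads for patient management and the sponsor's unblinded safety oversight stay as they are. If the U entries are simply an error in the table, the same edits correct it. If no overread is ever done, the edits have no effect on the analysis.

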Attachment 5. Protocol AACD Management of Infusion Reactions

Infusion Reaction Management Flowchart

Abbreviations: BP = blood pressure; IM = intramuscular; IV = intravenous; NSAID = nonsteroidal anti-inflammatory drug; PO = by mouth.

Continue supportive care in accordance with the symptoms/signs (Section 9.5.1.2).

Source: Adapted from Lichtenstein et al. 2015.

Attachment 6. Protocol Amendment I5T-MC-AACD(f) Summary

A Single- and Multiple-Dose Study to Assess the Safety, Tolerability, Pharmacokinetics, and Pharmacodynamics of Single and Multiple Intravenous Doses of LY3002813 in Patients with Mild Cognitive Impairment due to Alzheimer's Disease or Mild to Moderate Alzheimer's Disease

Overview

Protocol I5T-MC-AACD “A Single- and Multiple-Dose Study to Assess the Safety, Tolerability, Pharmacokinetics, and Pharmacodynamics of Single and Multiple Intravenous Doses of LY3002813 in Patients with Mild Cognitive Impairment due to Alzheimer’s Disease or Mild to Moderate Alzheimer’s Disease” has been amended. The new protocol is indicated by Amendment (f) and will be used to conduct the study in place of any preceding version of the protocol.

The overall changes and rationale for the changes made to this protocol are as follows:

- The cohort description in Section 7 has been updated to clarify that the patient numbers in each cohort are planned enrollment numbers, rather than a minimum required number of patients to complete the study.
- The duration of the follow-up period after administration of a single dose of 40 mg/kg LY3002813 has been reduced from 18 months to 6 months. The reduced follow-up period is attributable to emerging amyloid PET data in Cohorts 1 and 2 that indicate that follow-up PET scans up to 6 months will be sufficient to evaluate the effect of a single dose of 40 mg/kg LY3002813 on amyloid burden assessed using florbetapir PET. However, if the immunogenicity titer at the last scheduled assessment or discontinuation visit is positive, then additional safety assessments remain the same (see Section 10.4.1).
- Section 9.2.3 (18F-AV-1451 Dosage and Administration) has been amended to allow previously conducted 18F-AV-1451 PET scans to be used as the baseline scan.
- Minor editorial changes and formatting corrections were made but not necessarily documented below.

Revised Protocol Sections

Note:	All deletions have been identified by strikethroughs . All additions have been identified by the use of underscore .
--------------	---

2. Synopsis

Number of Planned Patients: Up to 150 patients may be enrolled so to ensure that approximately a minimum of 72 patients complete the study (7 dosing cohorts of 8 to 12, Eight patients) each in Cohorts 1, 2, and 3. Twelve patients each in Cohorts 4, 5, 6, and 7.	Phase of Development: 1b
Length of Study: Part A (Cohorts 1, 2, and 3): screening—approximately 6 weeks; single intravenous (IV) LY3002813 or placebo treatment; 72-week (for Cohorts 1 and 2) and 24-week (for Cohort 3) follow-up. Part B (Cohorts 4 and 5): screening—approximately 6 weeks; multiple dose IV LY3002813 or placebo treatment every 2 weeks (Q2W) for 24 weeks; 48-week follow-up after dosing. Part C (Cohorts 6 and 7): screening—approximately 6 weeks; multiple dose IV LY3002813 or placebo treatment every 4 weeks (Q4W) for 72 weeks; 12 weeks follow-up after dosing.	
Study Design: This is a 3-part, patient- and investigator-blind, randomized within cohort, placebo-controlled, parallel-group, single- and multiple-dose study in patients with MCI due to AD or mild to moderate AD to assess the safety, tolerability, PK, and PD of single and multiple IV doses of LY3002813. The study will be conducted in at least 7 cohorts. 
 • Cohort 1: 10 mg/kg IV single dose • Cohort 2: 20 mg/kg IV single dose • Cohort 3: 40 mg/kg IV single dose • Cohort 4: 10 mg/kg IV Q2W for 24 weeks • Cohort 5: 20 mg/kg IV Q2W for 24 weeks • Cohort 6: 10 mg/kg IV Q4W for up to 72 weeks • Cohort 7: 20 mg/kg IV Q4W for up to 72 weeks Each cohort will contain a minimum of approximately 6 (single dose) or 9 (multiple dose) patients treated with LY3002813 and 2 to 3 patients treated with placebo so that the study can detect target engagement and antidrug antibody (ADA) frequency relative to those observed in Study I5T-MC-AACC.	
Planned Duration of Treatment: Part A (Cohorts 1, 2, and 3): single dose of LY3002813 or placebo followed by 72 weeks (for Cohorts 1 and 2) and 24 weeks (for Cohort 3) follow-up for each dose level Part B (Cohorts 4 and 5): 13 doses of LY3002813 or placebo administered Q2W for 24 weeks followed by 48-weeks follow-up Part C (Cohorts 6 and 7): 19 doses of LY3002813 or placebo administered Q4W for 72 weeks followed by 12-weeks follow-up	

[figure not shown]
